2.3 Treatment Assignment and Blinding

Each subject who meets the eligibility criteria will be assigned open-label anifrolumab using an interactive voice/web response system. This study is not blinded.

2.4 Sample Size

Sample size estimation is based on the number of subjects who have completed the treatment period of study CD1013. A total of 307 subjects have been randomized in study CD1013. Assuming that 20% of subjects will be lost to follow up or discontinue from study CD1013, there will be a total of approximately 240 subjects who will be eligible for this long-term safety study.

3 STATISTICAL METHODS

3.1 General Considerations

Categorical data will be summarized by the number and percentage of subjects in each category. Continuous variables will be summarized by descriptive statistics, including mean, standard deviation, median, minimum, and maximum. Data will be provided in data listings sorted by treatment group and subject identification (SID) number.

Baseline will be defined as the last non-missing observation on or before Day 1 prior to investigational product administration of study CD1145.

3.1.1 Analysis windows

Analysis visit windows will be used for all scheduled assessments to map longitudinal observations to scheduled visits and thereby allow for by-visit analyses, since not all assessments are performed on the scheduled day. Unless otherwise specified, all longitudinal efficacy and safety data analyses will be based on the analysis visit windows. The analysis visit windows will be calculated by bisecting the interval between adjacent scheduled visit days and will be specified in the SPP.

The actual assessment day will be mapped to the windows defined for each scheduled study visit with following rules:

- If more than one assessment falls within a visit window, the closest non-missing assessment to the scheduled day will be used in the analysis.
- If two non-missing assessment actual dates are equidistant from the target day, the earlier visit will be used in the analysis.

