5.1.2 Treatment Period

The visit windows during the treatment period are \pm 7 days; however, in this long-term study, this may not always be possible; therefore, the IVRS/IWRS will be programmed to ensure that consecutive doses are administered more than 14 days apart, which will not be considered a protocol deviation.

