5.2.5 Clinical Laboratory Tests

Clinical laboratory safety tests will be performed in a central clinical laboratory. Urine pregnancy tests may be performed at the site using a licensed test (dipstick). Abnormal laboratory results should be repeated as soon as possible (preferably within 24 to 48 hours).

Subjects will be required to fast for at least 8 hours prior to the assessment of lipid profile (high-density lipoprotein [HDL], low-density lipoprotein [LDL], cholesterol, and triglycerides) according to the Schedule of Study Procedures (Table 5.1-1 and Table 5.1-2).

The following clinical laboratory tests will be performed (see Table 5.1-1 and Table 5.1-2 for the schedule of tests):

Serum Chemistry

- Calcium
- Chloride
- Potassium
- Sodium
- Aspartate transaminase (AST)
- Alanine transaminase (ALT)
- Alkaline phosphatase (ALP)

- Gamma glutamyl transferase (GGT)
- Blood urea nitrogen (BUN)
- Creatinine
- Total bilirubin (reflexively fractionated if elevated)
- Glucose
- Albumin
- Creatine kinase (CK)

Note for serum chemistries: Tests for AST, ALT, ALP, and total bilirubin must be conducted concurrently and assessed concurrently.

Hematology

- White blood cell (WBC) count with differential
- Red blood cell (RBC) count
- Hematocrit
- Hemoglobin

- Platelet count
- Mean corpuscular volume (MCV)
- Mean corpuscular hemoglobin concentration (MCHC)

Urinalysis

- Color
- Glucose

Ketones

Blood

- Appearance
- Specific gravity
- pH
- Bilirubin
- Protein
- Microscopy including WBC/high power field (HPF), RBC/HPF

Pregnancy Test (females of childbearing potential only)

• Urine human chorionic gonadotropin (HCG)

Note: Any female subject who is postmenopausal based on documented results from the serum follicle-stimulating hormone test will not require urine HCG tests in this study. Any female subject who feels that they have had a change in status to postmenopausal at any point during this study can request a serum follicle-stimulating hormone test. If the results show that the subject is postmenopausal, then the subject will not require any further urine HCG tests.

Additional Tests

- Lipid profile (HDL, LDL, cholesterol, triglycerides, direct LDL when triglycerides are > 400 mg/dL) requiring a fasting blood sample of at least 8 hours
- Immunology profile: ANA, extractable nuclear antigen (RNP, Sm, SSA, SSB), quantitative immunoglobulins

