3.8.5 Clinical Laboratory Evaluation

Hematology, serum chemistry, lipid profile (HDL, LDL, cholesterol, and triglycerides), and urinalysis parameters will be collected in this study. The hematology, serum chemistry, and lipid profile parameters as well as their changes from baseline will be summarized with descriptive statistics by visit. The shift from baseline in hematology, serum chemistry, lipid profile, and urinalysis parameters will be summarized by visit.

Treatment-emergent laboratory/vital signs changes (TELVC) will be defined for post-baseline values according to the reference ranges given in **Appendix E**. Number of subjects with TELVC will be summarized by visit.

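### By-visit laboratory tables can drop an abnormal value in favour of its repeat, and the SAP lacks for laboratory TELVC the all-measurements rule that it gives vital signs

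*SAP*

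**What the plan says.** Protocol 5.2.5 (Clinical Laboratory Tests) states "Abnormal laboratory results should be repeated as soon as possible (preferably within 24 to 48 hours". It is a recommendation, it sets no maximum lag, and it asks for no repeat of normal results.

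SAP 3.1.1 (Analysis windows) opens with "Analysis visit windows will be used for all scheduled assessments to map longitudinal observations to scheduled visits" and makes the windows the default: "Unless otherwise specified, all longitudinal efficacy and safety data analyses will be based on the analysis visit windows". On their width it says "The analysis visit windows will be calculated by bisecting the interval between adjacent scheduled visit days and will be specified in the SPP". Where several values compete, "If more than one assessment falls within a visit window, the closest non-missing assessment to the scheduled day will be used in the analysis", and for ties, "If two non-missing assessment actual dates are equidistant from the target day, the earlier visit will be used in the analysis". No precedence is given to the scheduled sample.

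SAP 3.8.5 (Clinical Laboratory Evaluation) sets no different rule for laboratory data. It says "The shift from baseline in hematology, serum chemistry, lipid profile, and urinalysis parameters will be summarized by visit" and also counts subjects with TELVC by visit. It describes no any-time or worst-value laboratory summary.

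SAP 3.8.6.1 (Vital Signs) handles multiple values differently. One pre-dose value feeds the by-visit tables, but every measurement counts towards TELVC. SAP 3.8.5 has no such sentence.

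**The concern.** A repeat under Protocol 5.2.5 is triggered by the result itself. The second value therefore exists mainly where the first was abnormal, and through recovery or regression to the mean it will tend to lie closer to normal. A rule that chooses between the two by calendar distance, without regard to which was the scheduled sample, can remove the abnormal value from the by-visit table. Whether it does so depends on whether the subject came a few days early or late, which has no clinical meaning.

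The hepatic tests show the overlap most clearly. For subjects with ALT/AST up to 2 × ULN at screening, Protocol Appendix 8 calls for an immediate repeat when ALT or AST is at least 3 but below 5 × ULN. SAP Appendix E sets the lower ALT and AST TELVC limit at 3 × ULN. The values that cross that limit are thus among those most likely to be drawn again.

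At stake are the shift tables, the by-visit means and, if built on windowed values, the laboratory TELVC counts. Protocol 7.3.1 lists these laboratory data among the supporting safety variables for the primary objective.

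**Working it through.** The plan gives no replacement rate to reproduce, so the rate is enumerated.

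**Inputs**
- Draw-day offset from target, *d*: on treatment, "The visit windows during the treatment period are" ±7 days (Protocol 5.1.2, which also tolerates wider deviations). Its distribution is not given and has to be assumed.
- Lag from draw to repeat, *k*: 1 or 2 days, the preferred range in Protocol 5.2.5.
- Window half-width: bisecting a 4-week interval gives 28/2 = 14 days, and a 12-week interval 84/2 = 42 days. The furthest repeat lies at 7 + 2 = 9 days, so it shares the window of its original.

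**Rule.** The repeat replaces the original if |*d* + *k*| < |*d*|, that is, if *d* < −*k*/2. A draw on or after target (*d* ≥ 0) always keeps the original. At *d* = −1 and *k* = 2 the two tie, and the earlier value stays.

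**Step 1: chance of replacement, given that a repeat is done**

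| Assumed draw days | *k* = 1 | *k* = 2 |
|---|---|---|
| Uniform, −7 to +7 | 7/15 = 46.7% | 6/15 = 40.0% |
| Triangular, weights 8 − abs(*d*) | 28/64 = 43.8% | 21/64 = 32.8% |
| Normal, SD 3 days | 43.3% | 30.6% |
| Normal, SD 2 days | 40.1% | 22.7% |
| Half on target, rest uniform | 0.5 × 7/14 = 25.0% | 0.5 × 6/14 = 21.4% |
| Normal, SD 1 day | 30.9% | 6.7% |
| All on or after target | 0% | 0% |

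Off-centre scheduling moves the rate a long way. With SD 2 days, visits averaging two days early give 77.3% and 59.8%; visits averaging two days late give 10.6% and 4.0%. Longer lags lower it: for uniform draws, a repeat after 4 days replaces 5/15 = 33.3%.

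**Step 2: chance that the abnormality disappears**

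Loss = P(repeat done) × P(replace) × P(repeat back within limits), treating the factors as independent. The documents give neither the first nor the third. Taking every abnormal value as repeated, an assumed one-third replacement rate, and 25%, 50% or 75% normalising:

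- 1/3 × 0.25 = 8.3%
- 1/3 × 0.50 = 16.7%
- 1/3 × 0.75 = 25.0%

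The same 25-75% range gives 0.467 × 0.25 = 11.7% to 0.467 × 0.75 = 35.0% at the top of the uniform case, and 0.067 × 0.25 = 1.7% to 0.067 × 0.75 = 5.0% at the bottom of the SD 1 day case. If only some abnormal results are repeated, each figure shrinks in proportion.

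**Step 3: under an all-measurements or worst-value rule** the original abnormal value cannot be displaced, so the loss is 0%.

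**The case against.** The strongest reply is that repeats may never enter the windows. SAP 3.1.1 introduces them for scheduled assessments and leaves the window limits to the statistical programming plan, which is not available here. This stands as a real uncertainty. It does not settle the matter: the selection rule speaks of more than one assessment in a window and excludes no kind of sample.

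A reader might infer that abnormal results must be repeated and that about a third of them vanish from the tables. The documents support neither. Protocol 5.2.5 says should; a one-third rate follows only from an assumed pattern of draw days; and a repeat that is still abnormal is still counted as abnormal.

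A reader might also infer that the rule can only lower abnormality counts. That goes too far. Unscheduled visits (Protocol 5.1.4) collect chemistry, hematology, lipids and urinalysis, with no condition that an earlier result was abnormal. An abnormal unscheduled value can therefore displace a normal scheduled one, and a worsening repeat can displace a milder value. The downward tendency is plausible because repeats are prompted by abnormal results, but it may be partly offset.

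Nor is it right to read this as undermining the primary safety conclusion. Protocol 7.3.1 rests mainly on TEAEs and TESAEs, with no formal testing, and the laboratory tables have a single treatment group (SAP 3.2.2). Laboratory findings that need action, or are judged beyond normal fluctuation, are reported as AEs (Protocol 6.1.1). Hepatic AESIs are captured throughout, listings retain every value, and the DSMB sees laboratory tables and listings. These safeguards stand, with one limit: nonserious AEs are generally captured only in year 1, so in years 2 and 3 the laboratory tables carry more of the record.

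Finally, giving the scheduled sample precedence over the closest one in descriptive tables is largely a matter of preference, and by itself would leave TELVC unresolved. The omission in SAP 3.8.5 is the firmer ground.

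**Conclusion.** The point holds as a gap in specification with a probable, unquantified downward effect on by-visit laboratory abnormality counts. It depends on unscheduled repeats being eligible for the windows. For draws centred on or after target and repeats after 1-2 days, replacement runs from 0% to about 47%, and higher if visits run early. The share of abnormalities actually lost is smaller, since it also needs the repeat to have been done and to have normalised. No single figure can be defended from the documents. What needs no assumption is the contrast within the SAP: all measurements count for vital-sign TELVC, nothing equivalent is said for laboratory TELVC, and no worst-value laboratory table is planned. The change is worth making because it is cheap and bears directly on the reported counts.

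**What to change.** In SAP 3.8.5:
- State that all post-baseline measurements, including unscheduled and repeat samples, are considered for laboratory TELVC, in line with SAP 3.8.6.1.
- Add a shift table from baseline to the worst post-baseline value, using all samples.

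In SAP 3.1.1:
- State whether unscheduled repeats are eligible for the by-visit descriptive tables. The closest-value rule may stay for those tables once this is explicit.

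The cost is a few sentences and one table, with no new data collection. Abnormality counts will become slightly less favourable, and a spurious value (a haemolysed sample, for example) will count unless it is flagged invalid, so the handling of invalid samples should be stated as well.

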3.2 Analysis Populations

3.2.1 Definition of Analysis Populations

The analysis populations are defined in Table 3.2-1.

Table 3.2-1 Analysis Populations

Population	Description
As-treated population	Subjects who receive any study investigational product in the OLE study will be included in the as-treated population.

All analyses will be performed on the As-treated population unless otherwise specified.

3.2.2 Treatment Groups for Analysis

Treatment group is Anifrolumab Total for all analyses except the exposure adjusted adverse event which will be summarized by Anifrolumab 300 mg, Anifrolumab 1000mg, and Anifrolumab Total.

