1.2.1 Product Derivation

1.2.2 Summary of Nonclinical Experience

1.2.3 Summary of Clinical Experience

MEDI-546 has been or is being investigated in 4 MedImmune/AstraZeneca-sponsored clinical studies in adult subjects with systemic sclerosis (SSc) or SLE. One study in SSc is complete (Study MI-CP180) and 3 studies in SLE, including the current study, are ongoing (Studies CD-IA-MEDI-546-1013, CD-IA-MEDI-546-1145, and D3461C00002).

Study CD-IA-MEDI-546-1013, a Phase 2b, randomized, double-blind, placebo-controlled, parallel-group study to evaluate the efficacy and safety of MEDI-546 in adult subjects with chronic, moderately-to-severely active SLE with an inadequate response to standard of care treatment for SLE, is currently ongoing and remains blinded. Enrollment in this study is complete. An interim analysis was conducted after the 210th randomized subject completed the Day 169 visit or discontinued from study treatment early. A total of 307 subjects have been randomized in a 1:1:1 ratio to receive a fixed IV dose of MEDI-546 (300 or 1000 mg) or placebo every 4 weeks (Q4W) for 48 weeks on Days 1, 29, 57, 85, 113, 141, 169, 197, 225, 253, 281, 309 and 337 for a total of 13 doses. There is an 85-day follow-up period in Study CD-IA-MEDI-546-1013, which the subjects must complete to be considered for enrollment into Study CD-IA-MEDI-546-1145.

Study D3461C00002, a Phase 2, multicenter, open-label, dose-escalation study to evaluate the safety and tolerability of MEDI-546 in adult Japanese subjects with active SLE, is

currently ongoing. Enrollment in this study is complete. A total of 17 subjects are receiving a fixed IV dose of MEDI-546 (100, 300, or 1000 mg) Q4W for 48 weeks for a total of 13 doses followed by a fixed IV dose of MEDI-546 (300 or 1000 mg) Q4W for 104 weeks for a total of 27 doses.

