2.3 Exploratory Objectives

3 STUDY DESIGN

3.1 Overview of Study Design

This is an open-label, multinational, multicenter study to evaluate the long-term safety and tolerability of MEDI-546 in adult subjects with chronic, moderately-to-severely active SLE who were previously treated with investigational product (MEDI-546 or placebo) and completed Study CD-IA-MEDI-546-1013 through treatment and follow-up. The study will be conducted in approximately 240 subjects at up to 100 study sites.

Once subjects have completed treatment and follow-up in Study CD-IA-MEDI-546-1013 (through Day 422), signed the informed consent form (ICF), and met all study eligibility criteria, they may be enrolled in this OLE study. The start of this OLE study (defined as the day [Day 1] the subject receives their first dose of open-label MEDI-546) should occur within 28 days of the Day 422 visit of Study CD-IA-MEDI-546-1013 (with the exception of those subjects in the regions of Donetsk and Lugansk in the Ukraine, where the political situation necessitated a suspension of study activities) or at the discretion of the medical monitor if the start of this OLE study occurs outside the 28-day window. All subjects will receive IV MEDI-546 as a 300 mg fixed dose administered as an IV infusion over at least 30 minutes Q4W starting at Day 1 (Week 0) for up to 3 years or until the sponsor discontinues development of MEDI-546 for SLE, whichever comes first. All subjects will be followed for 85 days after receiving their last dose of MEDI-546.

At every visit, the investigator will evaluate the subject's clinical status and perform a risk/benefit analysis based on clinical judgment to determine if the subject should continue to receive MEDI-546 in the study.

Figure 3.1-1 Study Flow Diagram

IV = intravenous

The endpoints to be measured in this study are described in Section 7.3.

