2.2 Study Design

This is an open-label, multinational, multicenter study to evaluate the long-term safety and tolerability of anifrolumab in adult subjects with chronic, moderately-to-severely active SLE who were previously treated with investigational product (anifrolumab 300 mg, 1000 mg, or placebo) and completed study CD-IA-MEDI-546-1013 (CD1013) through treatment (48 weeks dosing) and follow-up (85 days) periods. The start of this OLE study (first dose) should occur within 28 days of the last visit of study CD1013 or at the discretion of the medical monitor if the start of this OLE study occurs outside the 28-day window.

Approximately 240 subjects will be enrolled to receive IV anifrolumab as a 1000 mg fixed dose administered over at least 30 minutes every 4 weeks starting at Day 1 (Week 0) for up to 3 years or until the sponsor discontinues development of anifrolumab for SLE, whichever

[REDACTED]

comes first. The dose was changed to 300 mg on 12Feb2015 (protocol amendment 4) as the efficacy and safety data from study CD1013 indicated that the 300 mg dose had a more favorable benefit:risk profile than the 1000 mg dose. All subjects will be followed for 85 days after receiving their last dose of anifrolumab.

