3.6 Pharmacodynamic Endpoint and Analyses

3.6.1 Type I IFN Signature

The 21-gene type I IFN signature in whole blood will be used as a PD marker. The gene signature and the neutralization levels will be summarized by visit. Subgroup analysis of 21-gene type I IFN signature will be performed based on ADA status (positive vs negative).

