3.8.7 Subgroup Analyses

The treatment emergent AEs and SAEs will be summarized by 4-gene IFN signature (IFN high vs IFN low) and ADA status (positive vs negative).

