3.9 Immunogenicity

The IM results will be analyzed by summarizing the number and percentage of subjects who develop positive ADA. A descriptive summary of actual ADA titers by visit will also be provided.

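### SAP 3.2.2 pools ADA, PD, laboratory and vital-sign results over CD1013 arm, so first exposure cannot be told from re-exposure; descriptive prior-arm columns would separate them cheaply

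*SAP*

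**What the plan says.** **Grouping.** SAP 3.2.2 reads: "Treatment group is Anifrolumab Total for all analyses except the exposure adjusted adverse event". The excepted tables are shown for 300 mg, 1000 mg and Total, meaning dose received in the extension.

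**Who is pooled.** SAP 2.2 describes the subjects as "previously treated with investigational product (anifrolumab 300 mg, 1000 mg, or placebo". Protocol 1.2.3 says that CD1013 subjects were "randomized in a 1:1:1 ratio to receive a fixed IV dose of MEDI-546 (300 or 1000 mg) or placebo", for 13 doses, the last on Day 337. Under Protocol 3.1 the extension starts within 28 days of Day 422 of CD1013, "or at the discretion of the medical monitor if the start of this OLE study occurs outside the 28-day window". Two regions are also exempted from the window.

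**Baseline.** SAP 3.1 uses the last non-missing value up to Day 1 of the extension, before dosing, whatever the prior arm. SAP 3.8.5 and 3.8.6.1 then summarise change from that baseline by visit for laboratory values and vital signs. SAP 3.6.1 summarises PD levels by visit; no PD change from baseline is stated in the visible text.

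**ADA.** Immunogenicity is the secondary objective. SAP 3.9 analyses it by "summarizing the number and percentage of subjects who develop positive ADA" and adds a summary of titres by visit. Protocol 5.1.2.1 includes a predose ADA sample at Day 1. ADA status also defines subgroups. For PD, SAP 3.6.1 says "Subgroup analysis of 21-gene type I IFN signature will be performed based on ADA status (positive vs negative"). For treatment-emergent AEs and SAEs, SAP 3.8.7 says they "will be summarized by 4-gene IFN signature (IFN high vs IFN low) and ADA status (positive vs negative"). Neither section gives the time point at which status is determined.

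**The concern.** An ex-placebo subject's baseline is drug-naive, and the first extension infusion is the first exposure. A subject from an active arm has a baseline taken some three months after a course of up to 13 doses, and the first extension infusion is a re-exposure. ADA development and change from baseline are different quantities in these two groups. One pooled column averages them with weights fixed by how many subjects came from each arm.

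What is at stake is information. The ex-placebo group can add up to 156 weeks of observation from first exposure. A Total-only display does not allow a reader to recover ADA incidence or laboratory change in that group, or to see whether it differs from the re-exposed group. No visible subgroup does this: the planned ones use ADA status and 4-gene IFN signature.

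A smaller related gap is that SAP 3.9 does not say how subjects already ADA-positive at Day 1 are counted, or what the denominator is.

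**Working it through.** **1. The plan's own sample size.** SAP 2.4 starts from 307 randomised in CD1013: "Assuming that 20% of subjects will be lost to follow up or discontinue from study CD1013". 307 × (1 − 0.20) = 245.6, consistent with the stated figure of approximately 240.

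**2. Size of the two groups.** The 1:1:1 allocation with equal retention (assumed) gives 240/3 = 80 ex-placebo and 160 pre-exposed. If placebo-arm retention is 70% to 90% and the total stays at 240, then 307/3 × 0.70 = 72 and 307/3 × 0.90 = 92 ex-placebo subjects, or 30% to 38% of 240.

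**3. Timing of baseline in pre-exposed subjects.** Day 422 − Day 337 = 85 days after the last scheduled dose, and 85 + 28 = 113 days at the end of the start window. This ignores visit windows. No upper limit is stated when the medical monitor allows a later start. Lipids are an exception: Protocol Table 5.1-1 and 5.1.2.1 show no Day 1 lipid sample, the first being at Week 4, so any lipid baseline must come from CD1013 or be missing.

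**4. What pooling does to ADA incidence (illustration).** The documents give no ADA rates, so all rates here are assumed. Pooled percentage = (rate in ex-placebo × 80 + rate in pre-exposed × 160)/240, with no Day 1 positives.

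| New ADA, ex-placebo | New ADA, pre-exposed | Pooled |
|---|---|---|
| 5% | 0% | 4/240 = 1.7% |
| 2% | 2% | 4.8/240 = 2.0% |
| 10% | 2% | 11.2/240 = 4.7% |
| 0% | 5% | 8/240 = 3.3% |

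The pooled figure may lie below, at or above the first-exposure rate.

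**5. What the Day 1 rule does (illustration).** Take the first row and assume 10% of the 160 pre-exposed subjects, that is 16, are positive at Day 1. New positives over all subjects: 4/240 = 1.7%. New positives over Day 1 negatives: 4/224 = 1.8%. Any positive over all subjects: 20/240 = 8.3%. The choice of denominator matters little; whether Day 1 positives enter the numerator matters a good deal.

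**6. What a split could show.** About 80 subjects per column gives standard errors √(240/80) = 1.73 times those of the pooled column. The 95% half-width for a difference in mean change between two arm columns is 1.96 × √(2/80) = ±0.31 SD. Placebo against both active arms combined gives 1.96 × √(1/80 + 1/160) = ±0.27 SD. Both are before extension dropout; at an assumed 60% retention (48 per arm) the pairwise figure is 1.96 × √(2/48) = ±0.40 SD. For ADA, 4 positives in 80 has an exact 95% interval of 1.4% to 12.3%, and 0 in 80 has an upper limit of 4.5% (two-sided).

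**The case against.** The case for leaving the plan alone is substantial. The study is open-label and descriptive, with no formal testing (Protocol 7.3.1). Its objectives are long-term safety and immunogenicity, and none compares first-exposed with re-exposed subjects. First exposure was already observed in the two active arms of CD1013. On these grounds a prior-arm display is an addition, not a correction of an error. That stands, and it limits the point to a cheap improvement.

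Several stronger readings are tempting and are not supported:

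- *The planned ADA percentage is inflated by Day 1 positives.* The verb in SAP 3.9 most naturally means newly positive, which would exclude them. The 8.3% above needs the less natural reading as well as an assumed Day 1 rate. The wording should be settled, but it does not establish inflation.
- *Pooled changes from baseline are biased in a known direction.* No visible passage shows that laboratory or vital-sign values 85 days or more after the last dose still differ by prior arm. Comparisons between arms would also be among subjects who, with limited exceptions, completed CD1013, so selection may contribute to any difference.
- *Baseline differences distort who has a vital-sign TELVC.* In SAP Appendix F each criterion with a change from baseline is nested within the absolute limit beside it, so baseline cannot alter who meets any criterion.

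The SAP also refers table templates and specifications to a separate programming plan that is not public, and some SAP text is redacted. ADA status could be defined there. Prior-arm columns are less likely to be there, because SAP 3.2.2 is an explicit rule the other way.

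**Conclusion.** The point holds as a cheap improvement. SAP 3.2.2 expressly pools about 80 first-exposed subjects with about 160 subjects already given up to 13 doses; those counts assume equal retention, and 72 to 92 ex-placebo is a reasonable range. The consequence is a loss of information: ADA incidence on first exposure and change from a drug-naive baseline cannot be read from the planned tables. The 1.7% against 5% example shows how much one pooled figure could conceal under assumed rates; it does not predict what the data will show.

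A reader might infer that the tables fail the study's objectives or that their results are wrong. The documents support neither. The missing ADA definitions would be only a matter of clarification on their own, since titres by visit, including Day 1, are already covered. They are worth settling in the same revision because ADA status also defines the AE and PD subgroups.

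**What to change.** 1. In SAP 3.2.2, add columns by CD1013 randomised arm (placebo, 300 mg, 1000 mg) beside Total for the ADA, PD, laboratory and vital-sign tables. Label them descriptive, with no testing between columns.
2. In SAP 3.9, count as having developed ADA only subjects who were ADA-negative at extension Day 1, use those subjects as the denominator, and report the number positive at Day 1 separately.
3. In SAP 3.6.1 and 3.8.7, state the time point that defines ADA status (for example Day 1, any time, or newly positive after Day 1), consistently with SAP 3.9.
4. If the programming plan already holds any of this, cite it in the SAP.

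The cost is SAP wording, a merge of the CD1013 arm into the analysis data and wider tables. Day 1 ADA is already collected. The arm columns will be less precise than Total, as set out in step 6 of the working, and should be read with that in mind.

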1.3 Research Hypothesis

The research hypothesis is that neutralization of IFN signaling through the human type I IFN receptor with MEDI-546 in subjects with chronic, moderately-to-severely active SLE is safe and well tolerated when administered at a fixed dose of 300 mg Q4W.

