4.5.3 Treatment Regimen

Subjects will receive MEDI-546 300 mg administered as an IV infusion Q4W starting at Day 1 (Week 0) or the visit following approval of this amendment (for those subjects who

have already been dosed in this study) for up to 3 years or until the sponsor discontinues development of MEDI-546 for SLE, whichever comes first.

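### By-visit PD, ADA-titer, laboratory and vital-sign tables pool 1000 mg and 300 mg while the 300 mg share rises to 100% in year 3, so dose and time cannot be told apart in them

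*SAP*

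**What the plan says.** **Reporting groups.** SAP 3.2.2: "Treatment group is Anifrolumab Total for all analyses except the exposure adjusted adverse event which will be summarized by Anifrolumab 300 mg"; the sentence goes on to name 1000 mg and Total. Every other analysis has one pooled column.

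**By-visit tables under that rule.** For PD, SAP 3.6.1 says "The gene signature and the neutralization levels will be summarized by visit", with a subgroup split by ADA status only. For immunogenicity, SAP 3.9 says "A descriptive summary of actual ADA titers by visit will also be provided". Laboratory values (SAP 3.8.5) and vital signs (SAP 3.8.6.1) are also tabulated by visit, with change from baseline. SAP 3.9 plans the ADA-positive percentage too, but does not say that it is by visit.

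**Dose history.** SAP 2.2: "Approximately 240 subjects will be enrolled to receive IV anifrolumab as a 1000 mg fixed dose", and then "The dose was changed to 300 mg on 12Feb2015 (protocol amendment 4"). Under Protocol 4.5.3, 300 mg starts on Day 1 or, for subjects already dosed in this study, at "the visit following approval of this amendment". The Amendment 4 summary in Protocol Section 15 records that the same amendment lengthened treatment from two years to three. SAP 3.8.4 expects some subjects to have received both doses.

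**Target dose.** The hypothesis in Protocol 1.3 is that receptor blockade "is safe and well tolerated when administered at a fixed dose of 300 mg Q4W".

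**Where 300 mg does appear.** SAP 3.3.3 counts doses given at 300 mg, and SAP 3.8.4 gives exposure-adjusted AE rates in a 300 mg column.

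**The concern.** Each already-dosed subject switched at the first visit after approval, so the study week of the switch differs between subjects. Early visits can contain samples taken on 1000 mg; year-3 visits essentially cannot. In a pooled by-visit table, study week and current dose therefore move together.

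The study is descriptive, and Protocol 7.3.1 rules out formal testing, so these tables are how PD, titer, laboratory and vital-sign results will be read. A fall in neutralization or a laboratory shift across visits could reflect the change of dose and be taken for an effect of long treatment. The opposite error is also possible: a real drift could be offset by the dose reduction and missed, which matters when long-term safety is the primary objective. Immunogenicity is the secondary objective, and neither it nor the laboratory data has a 300 mg column.

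The issue is the dose received in the extension, not the arm of the parent study.

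**Working it through.** **1. The plan's own figure.** SAP 2.4 starts from 307 randomised subjects and assumes a 20% loss: 307 × (1 − 0.20) = 245.6, consistent with the stated approximate 240. No power or effect-size figure exists to reproduce.

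**2. When the mix must be all 300 mg.** Before Amendment 4 the treatment period was two years, so the last visit possible under the old dose was Week 104. Later infusions exist only under Amendment 4 and are 300 mg. A predose sample at Week 108 may still follow a 1000 mg infusion at Week 104. For samples, Week 120 is the safer point; it is also the first scheduled PD and ADA sample after Week 104 (Protocol Table 5.1-1).

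**3. Share on 300 mg at earlier visits.** The documents give neither enrolment dates nor the number starting on 300 mg, so this step is assumption. Let f be the share who start on 300 mg, and let the rest switch at a week spread evenly from a to b, with b no later than 104:

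p(t) = f + (1 − f) × (t − a)/(b − a), with the fraction held between 0 and 1.

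**4. Effect on the pooled mean.** Let D be the mean at 300 mg minus the mean at 1000 mg, constant and immediate, with no dropout, and let T be the true change over time. Then the pooled change from Week 12 to Week 144 = T + D × [p(144) − p(12)]. The last column below sets T = 0.

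| f | a–b (weeks) | Wk 12 | Wk 48 | Wk 72 | Wk 96 | Wk 120 on | Apparent change |
|---|---|---|---|---|---|---|---|
| 0% | 0–104 | 12% | 46% | 69% | 92% | 100% | 0.88 D |
| 20% | 0–104 | 29% | 57% | 75% | 94% | 100% | 0.71 D |
| 0% | 24–104 | 0% | 30% | 60% | 90% | 100% | 1.00 D |
| 0% | 52–104 | 0% | 0% | 38% | 85% | 100% | 1.00 D |
| 0% | 0–52 | 23% | 92% | 100% | 100% | 100% | 0.77 D |
| 40% | 0–52 | 54% | 95% | 100% | 100% | 100% | 0.46 D |

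Example, last row: p(12) = 0.40 + 0.60 × 12/52 = 0.54; p(144) = 1; difference 0.46.

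Across these patterns the 300 mg share is 0–54% at Week 12 and 0–95% at Week 48.

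**5. Masking.** The pooled change is zero whenever T = −D × [p(144) − p(12)]. With the first row, a true drift of −0.88 D would disappear.

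**6. With dose columns.** Under the same assumptions and T = 0, the change within each dose column is 0.

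**The case against.** **300 mg is described elsewhere.** A reader might infer that the plan never describes 300 mg. That is not so. The SAP counts 300 mg doses and reports 300 mg AE rates, and Protocol 7.3.1 assesses safety primarily through adverse events, with laboratory tests and vital signs as other variables. Late year-3 rows are also 300 mg in practice, although in subjects with differing earlier 1000 mg exposure. What stands is narrower: none of the PD, ADA, laboratory or vital-sign tables separates 300 mg.

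**No dose difference is shown.** A reader might infer that the tables will show a false trend. They can, but only if D is not zero. The documents do not quantify D for these variables, and the dose ratio of 1000/300 = 3.3 is not a response ratio. SAP 2.2 does say that the parent-study data gave 300 mg the better benefit-risk profile, so equal behaviour cannot be taken for granted.

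**The early mix is unknown.** A reader might infer that early visits are mostly 1000 mg. Protocol 4.5.3 allows a 300 mg start on Day 1, so this is not established.

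**ADA incidence.** The positive percentage is not stated as by visit. The time argument reaches titers only; for incidence the issue is pooling.

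**Dose columns bring their own confounding.** Before all have switched, the 300 mg column holds later enrollees and the 1000 mg column earlier ones. Membership changes from visit to visit, and a sample soon after the switch carries over 1000 mg exposure. All of this stands. It calls for a footnote; it is not a reason to leave dose and time fully mixed.

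**Conclusion.** The point holds in a limited form and is worth correcting, though it does not put the primary analysis at risk. The documents establish that the by-visit PD, ADA-titer, laboratory and vital-sign tables pool the two extension doses, that the 300 mg share reaches 100% of infusions after Week 104 (safely Week 120 for samples), and that no planned table separates dose from time for these variables. SAP version 2.0 is dated 26Oct2017, well after the switch, and already splits dose counts and AE rates by dose, so the omission is inconsistent within the SAP itself.

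The size is conditional: about 0.46 D to 1.00 D of apparent change between Weeks 12 and 144, for an unknown D. This rests on assumed enrolment and switch patterns, a constant and immediate dose difference, and no dropout. Dropout could shift the by-visit values as well.

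**What to change.** In SAP 3.2.2, add that the by-visit tables of 21-gene signature and neutralization, ADA titers, laboratory values and vital signs are shown by the dose at the last extension infusion before the sample (1000 mg, 300 mg) next to Total, with n in each cell. The baseline row has no earlier extension infusion and stays under Total.

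Add a footnote that the dose columns are not a randomised comparison, that they differ by enrolment cohort, that their membership changes across visits, and that early 300 mg samples may reflect earlier 1000 mg exposure.

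Do not assign ADA incidence to the dose before the first positive sample. Sampling is every 12 weeks up to Week 48 and every 24 weeks from Week 72 to Week 144, so an antibody that arose on 1000 mg may first be found after the switch; nor would such a rule define a denominator. Keep incidence as Total, or show it separately for subjects who received only 300 mg in the extension.

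Cost: SAP wording, two extra columns and some programming. SAP 3.8.4 already needs the date of the first 300 mg dose, so no new data are required. The downside is small cells at some visits, and switchers who appear in different columns over time.
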